##### NINDS-CDE Recommended Assessments for PD-Specific Clinical Features (only for on-state)

1. Demographics
2. PD Medical History
3. PD Family History
4. PD and Non-PD Medication Log
5. Motor: MDS-UPDRS parts I-IV
6. Psychiatric: Structured clinical interview for DSM-IV-TR (SCID) axis I disorders, research version, non-patient edition (29)
7. Cognitive: Montreal Cognitive Assessment (MoCA)(31)
8. Other non-motor: Non-motor Symptoms Questionnaire (NMS-Quest)(35) and the Scales for Outcomes in Parkinson's disease autonomic dysfunction scale (SCOPA-AUT)(32,33)
9. Quality of life: 8-item Parkinson's Disease Questionnaire (PDQ-8)(34)
10. Questionnaire for Impulsive-Compulsive Disorders in Parkinson's Disease(QUIP)(47)

11. Neo Five-Factor Inventory(48)

12. Rapid Assessment of Physical Activity(RAPA)(49)

For objective 2:

The intervention will be 8 weeks in duration and include a 4-week dosage titration period and a 4-week maintenance period. Transdermal patch. Dosing will begin at baseline on day zero with either 1) placebo or 2) rotigotine at 2mg/24h and will be increased following the recommended dose escalation schedule for PD such that subjects will increase to 4mg/24hrs in week 2, and 6mg/24hrs in week 3. This dose of rotigotine is within the range shown to be safe and efficacious for the treatment of motor symptoms. 17,36,37) The timing of assessments is shown in Table 1. All assessments except for the physical exam, and the Clinical Global Impression for Anxiety Severity and change scales (CGI-S and CGI-C)(38) are part of the CAPSIT-PD on- and off-state testing battery, the table indicates administration points. Safety and tolerability will be assessed by recording adverse events.

b. Study duration and number of study visits required of research participants.

Objective 1 is one 3-hour cross-sectional visit, duration and visits for objective 2 are in Table 1

Table 1. Assessment schedule for objective 2					
Visit Number	Screening	Baseline	Follow-up visits		
Time	- - -	0	WK2	WK4	WK8: FINAL
Diagnostic Interview or AIM 1 Battery	X				X
Physical Examination	X				X
MDS-UPDRS I-IV	X				X
MoCA	X				X
CGI-Severity	X	X			
CGI-Change			X	X	X
HAM-A	X	X	X	X	X
HAM-D	X	X	X	X	X
SCOPA-AUT, NMS	X	X	X	X	X

c. Blinding, including justification for blinding or not blinding the trial, if applicable.

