For the clinical trial in objective 2: double-blinded, randomized, placebo controlled, 8-week intervention study of rotigotine vs. placebo for the treatment of anxiety in PD. The study is double-blinded to reduce the risk of bias in rating anxiety response to treatment as both the subject and investigators will be rating anxiety using self-reports and investigator-administered scales.

d. Justification of why participants will not receive routine care or will have current therapy stopped.

Patients will receive routine care and will NOT have current therapy stopped.

e. Justification for inclusion of a placebo or non-treatment group.

Absence of current standard treatment for anxiety in PD justifies inclusion of a placebo group. Anti-anxiety drugs based on serotonin, norepinephrine, and benzodiazepine mechanisms are the current standard in non-PD populations and are used in PD without sufficient evidence of efficacy and may be associated with side effects.

f. Definition of treatment failure or participant removal criteria.

Rotigotine is an evidence based treatment for motor symptoms and motor complications of treatment in PD and deemed to be of "acceptable risk without specialized monitoring".(17) Rotigotine does carry the risk of nausea, vomiting, application site reactions, dizziness, anorexia, hyperhidrosis, insomnia, lower extremity edema, somnolence and dyskinesia. Rotigotine is a treatment routinely used as part of clinical care in PD. If impulse control disorders occur the subject will taper and stop the study drug, their treating neurologist will be notified, and they will be referred for psychiatric treatment. Subjects will be examined for lower extremity edema at screening and at each follow-up visit. If edema occurs subjects will be asked if they wish to discontinue the study drug. Subjects will be asked about excessive somnolence at each visit. If somnolence is severe and interferes with daily functioning, tapering and discontinuation of the study drug will be recommended.

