Subjects in the intervention study will be medically screened prior to enrollment and will be monitored at the designated intervals for any adverse events. Subjects who are acutely suicidal or an imminent risk to themselves will be excluded. Subjects will be removed from the study if they request removal, if the team believes it is unsafe to continue, if they experience significant distress for any reason, or if the patient becomes imminently suicidal. Subjects will be monitored closely by an experienced clinical team, available 24-hours per day.

g. Description of what happens to participants receiving therapy when study ends or if a participant's participation in the study ends prematurely.

After termination of the intervention study, prematurely or scheduled, a summary letter will be sent to the patient's treating clinicians detailing the patient's participation in the study, the patient's response, aftercare plans, and any other relevant information. The study medication or placebo will be tapered and stopped, unless, in the case of participant on study drug, their treating doctor wishes to continue rotigotine and take over prescribing it as part of their routine care. Subjects will be offered follow-up psychiatric care in our clinic as well as assistance in obtaining care elsewhere, including by providing consultation to their primary clinician/neurologist. All adverse events will be reported to the JHH IRB.

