For objective 2: The primary outcome variable is the HAM-A. Power was calculated based on an enrollment of 60 subjects total, equally distributed between treatment and control groups, with a 10% dropout by the final time-point, and a standard deviation of 8.55 (which is a pooled estimate calculated from different anxiety subtypes in PD patients assessed using the HAMA).(43) The within subject/between time-point correlation was assumed to be 0.5 with a compound symmetric correlation structure, and the alpha level was set at .05. Power calculations were based on the formula of Jung and Ahn,(44) which calculates power for the difference in slope (i.e. the difference in response trajectory) between treatment and control groups for a longitudinal clinical intervention. Based on the assumptions specified, we would be able to detect an effect size of .69 from baseline to 8 weeks for the two groups with 80% power. This proposal is for a proof of concept study that will provide important initial estimates which may be used to 1) assess the potential efficacy of this novel anxiety intervention and thus provide necessary data for a "go-no-go" decision for a more definitive hypothesis-testing trial, and 2) provide estimates of effect size and variance needed to properly design such a trial.

Screening for objective 1: Screen failures are expected to be rare for objective 1 as there are only 3 criteria for exclusion: 1) UK Brain Bank criteria for PD, 2) English speaking, and 3) nondemented. In our longitudinal study of Parkinson's disease, which has autopsy confirmation at study end, the rate of accurate clinical diagnosis of PD is approximately 90%. The presence of dementia has a similar accuracy and will be further screened using the MoCA with a cut off of <23. The drop-out rate is also expected to be low as objective 1 takes place in one 3-hour visit. Screening for objective 2: Objective 2 will require 60 subjects who *can* be recruited from the n=200 from objective 1. Based on our preliminary data, 30% of subjects with a DSM anxiety disorder and comorbid depression and up to 53% with anxiety disorders only will not be

on any treatment for anxiety. In addition, we have included a protocol for enrolling individuals whose anxiety is not adequately controlled on their current therapy.(item 4 inclusion criteria)

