Subjects for objective 2 will be preferentially recruited from objective 1 for maximum efficiency. In the unlikely event that none of the subjects for objective 2 come from objective 1 the total number of subjects needed for both is n=260. We will be conducting post consent screening and will allow for ~15% screen fail rate and estimate that the maximum number of subjects consented will not exceed 300.

d. Early stopping rules.

Participants will be removed from the study if they request removal, if the team believes it is unsafe to continue, if they experience significant distress for any reason, or if the patient becomes imminently suicidal. Subjects will be monitored closely by an experienced clinical team, available 24-hours per day.

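### Removing subjects from the study for distress, with no HAM-A at or after exit, can make missing primary-outcome data informative and bias the effect estimate in a direction not known in advance

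*Combined protocol and SAP*

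**What the plan says.** Section 4f (treatment failure and participant removal) ends a subject's time in the study on request, for safety, for imminent suicidality, or "if they experience significant distress for any reason". Section 7d repeats this under early stopping rules: "Participants will be removed from the study if they request removal, if the team believes it is unsafe to continue", with the distress criterion following. The rotigotine paragraph of section 8a repeats it again. Distress is not defined.

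Other events in section 4f lead only to stopping study drug. For impulse control disorders: "If impulse control disorders occur the subject will taper and stop the study drug". For severe somnolence, "tapering and discontinuation of the study drug will be recommended". For edema, the subject is asked whether to discontinue the drug. None of these says that the subject leaves the study.

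On what follows an early exit, section 4g says: "After termination of the intervention study, prematurely or scheduled, a summary letter will be sent to the patient's treating clinicians". It adds a taper and an offer of psychiatric follow-up, but no rating. On the assessment schedule, section 4a says "The timing of assessments is shown in Table 1"; that table has HAM-A at screening, baseline and weeks 2, 4 and 8, and no early-termination visit.

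Section 7c states: "The primary outcome variable is the HAM-A". The sample size is worked out "with a 10% dropout by the final time-point", without cause or arm. For objective 2 it names no analysis model, analysis population or missing-data method. The GEE slope formula is cited for power only.

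**The concern.** Table 2 admits subjects with a DSM anxiety disorder for which medication is indicated. They must not be on anti-anxiety therapy, or must be tapered off it, except where it is given for another indication. Current psychotherapy for anxiety or depression excludes them. Half then receive placebo. Worsening anxiety is therefore an obvious route to significant distress, and distress triggers the more complete of the plan's two kinds of exit.

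If HAM-A stops at that point, whether a score is missing depends on something close to the score itself, and may do so differently in the two arms. Section 7c describes the trial's product as estimates of effect size and variance for a go/no-go decision. With 30 per arm, a handful of such exits falls directly on that estimate.

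**Working it through.** **1. Inputs.** From section 7c: N = 60 (30 per arm), SD 8.55, correlation 0.5 with compound symmetry, alpha 0.05 (taken as two-sided), 80% power, 10% dropout, effect size 0.69. In points, 0.69 × 8.55 = 5.90.

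**2. The plan's own figure.** In SD units the slope formula is

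SE = √{ΣΣ p_jk r_jk d_j d_k / [0.25 N (Σ p_j d_j²)²]}

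Here p_j is the fraction still observed at visit j, p_jk the smaller of p_j and p_k, r_jk the correlation (1 when j = k, otherwise 0.5), and d_j the visit time minus its p-weighted mean. The detectable effect is (1.960 + 0.842) × SE × follow-up length.

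- Five equally spaced ratings with loss rising evenly to 10%: Σp d² = 9.487 and the double sum is 5.068, so SE = √[5.068/(15 × 9.487²)] = 0.0613 and the effect is 2.802 × 0.0613 × 4 = 0.687. This reproduces 0.69.
- Weeks 0, 2, 4, 8 without loss: Σd² = 35 and the double sum is 17.5, so SE = √[17.5/(15 × 35²)] = 0.0309 and the effect is 2.802 × 0.0309 × 8 = 0.692.
- Weeks 0, 2, 4, 8 with 10% loss: 0.734.

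**3. Anxiety-driven removal, same rule in both arms.** Simulation with the section 7c SD and correlation, visits at weeks 0, 2, 4 and 8, and a true effect of 5.90. Assumed: removal at the first visit where HAM-A is at least 12 points above baseline, that score not recorded, and a 4-point placebo improvement.

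| Removal possible at | Lost, placebo / rotigotine | GEE, independence | GEE, exchangeable | Likelihood | Completers |
|---|---|---|---|---|---|
| weeks 2 and 4 | 10.0% / 6.2% | 5.92 | 5.79 | 5.75 to 5.80 | about 5.6 |
| weeks 2, 4 and 8 | 11.6% / 6.5% | – | 5.57 | 5.51 | about 5.3 |

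Overall loss is (10.0 + 6.2)/2 = 8.1% and (11.6 + 6.5)/2 = 9.05%. For GEE and likelihood the bias runs from none (5.92) to (5.90 − 5.51)/5.90 = 6.6%. For completers it reaches (5.90 − 5.3)/5.90 = 10%. In subjects, the first row is 30 × 0.100 = 3 against 30 × 0.062 = 1.9.

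With a 3-point placebo improvement and week-8 scores also lost (13.0% / 7.1%), independence GEE gives 5.70, likelihood 5.50 and completers 5.21: attenuation of 3%, 7% and 12%.

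**4. Removal mainly on rotigotine.** Assumed thresholds: a 20-point rise on placebo against 6 or 4 on rotigotine, score not recorded. Loss is 2.6% against 30% to 39%. Likelihood gives 6.92 to 7.32, away from zero, and independence GEE 6.01 to 6.11. These losses are far above the planned 10%; the runs show direction, not expected size. With 12 against 8 points (18.0% / 21.6% lost) the estimates are 5.57 (GEE) and 5.69 (likelihood). So a modest excess of removals on rotigotine does not by itself reverse the sign.

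**5. No true effect.** The same threshold in both arms with about 26% lost in each gives an estimate of about 0.

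**6. HAM-A recorded at removal.** GEE and likelihood estimates return to about 5.9 in the runs of both step 3 and step 4. In the step 3 runs, completers-only estimates stay low even then, at about 5.6.

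**The case against.** Four points can be made against the concern.

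- **Distress for any reason is not the outcome.** Section 4f lists nausea, dizziness, insomnia, somnolence, dyskinesia and other effects of rotigotine, any of which could cause distress. A reader might infer that the rule ends HAM-A collection because of the outcome and so pulls the effect towards zero. The documents do not support that: they do not tie distress to HAM-A and give no removal rates by arm. This objection stands, and the direction must be left open.
- **The bias is small at the planned loss.** Week 8 is the final visit and HAM-A is scheduled there, so a subject removed at that visit has little left to miss. With removal limited to weeks 2 and 4 the likelihood bias is 0.10 to 0.15 points. The standard error implied by 80% power is 5.9/2.80 = 2.1 points, so 0.15 points is 0.07 standard errors. This also stands. Claims of a serious loss of power depend on deleting week-8 scores or on loss well above 10%.
- **Nothing says that the rating is skipped.** HAM-A is scheduled at weeks 2, 4 and 8, and section 4g reports the patient's response to clinicians after an early exit, which suggests some exit evaluation. The end of HAM-A collection is indeed an inference from removal and silence. But removal can fall between visits, section 8a has the examiner stop an evaluation in which distress is reported, and section 4g names no scale.
- **No analysis is specified to criticise.** True: GEE is named for power only. That leaves the loss without any stated safeguard.

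**Conclusion.** The point holds as a risk of informative missingness of unknown direction. It rests on the wording of sections 4f, 7d and 8a, on the contrast with the drug-only stopping rules, and on the absence of an exit or later HAM-A in Table 1 and section 4g.

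The trigger, the placebo change and the split of losses between arms are assumptions. At 8 to 9% overall loss they give a bias of about 0 to 7% for GEE or likelihood analyses and up to about 10% for completers. That is modest beside the sampling error of 60 subjects. It would grow with heavier loss, and could reverse under a likelihood model if rotigotine distress dominated. The documents do not support a firm claim that the effect is biased low, or that power falls by a stated amount. The change is still worth making: it is cheap, and in the simulations recording HAM-A at removal dealt with both directions.

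**What to change.** Leave the clinical removal criteria as they are; whether distress should end treatment is not a statistical matter. Change what happens to assessment:

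- In sections 4f, 7d and 8a, separate stopping study drug from ending assessment, and say which one each criterion triggers.
- Add an early-termination column to Table 1 with HAM-A, HAM-D and CGI-C at the removal visit, where the subject agrees and the clinician finds it acceptable.
- In section 4g, invite consenting subjects to the remaining scheduled visits up to week 8.
- Record the reason for each removal while blinded, and tabulate reasons by arm.
- In section 7c, name the objective 2 analysis: all randomised subjects, all recorded HAM-A, not completers only. Add a sensitivity analysis that lets missing scores be worse than predicted in either arm.

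The cost is protocol and analysis wording and a few extra ratings. One consequence should be stated: scores taken after study drug is stopped make the estimate a treatment-policy effect, which may be smaller than the effect while on drug. A side benefit is that full follow-up on the Table 1 weeks brings the detectable effect from 0.734 back to 0.692.

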## 5. Inclusion/Exclusion Criteria

Subjects for both objectives will be English-speaking adult men and women including minority groups, ages 21 years or older, with idiopathic PD, based on UK Brain Bank Criteria.(39) Subjects with a diagnosis of dementia or a Montreal Cognitive Assessment (MoCA) (30) <23 will be excluded to reduce the chance of enrolling individuals with Lewy body dementia. Additional inclusion and exclusion criteria for objective 2 are in Table 2.

Table 2. Additional inclusion and exclusion criteria for objective 2 8-week intervention study
---

Inclusion Criteria
--------------------

1. Diagnosis of DSM Anxiety Disorder and as part of this intervention study, we will include all anxiety subtypes provided treatment with medication is indicated in standard clinical psychiatric practice
2. Stable medical history and general health. If non-postmenopausal female, must be non-pregnant and using a medically acceptable form of contraception during the study if sexually active
3. On stable anti-parkinsonian therapy for 2 weeks before enrollment and expected to be able to remain on stable therapy for the 8-week study.
4. If treated for depression, must be on stable anti-depressant for 2 weeks before enrollment and expected to be able to remain on stable therapy for the 8-week study.
5. \*[Not on anti-anxiety therapy (unless it is for another indication, i.e. REM Sleep Behavior Disorder) at time of enrollment OR able to be tapered safely off these medications as determined by the t ½ of prescribed medication at the time of screening]\*

#### Exclusion Criteria

1. \*[Exclude subjects with dementia as diagnosed by DSM criteria or MoCA <23 and subjects with less than a 1 year duration of PD to help exclude subjects who may have Lewy body dementia (62)]\*
2. Lifetime diagnosis of schizophrenia, bipolar disorder, impulse control disorder (ICD), or major depression with psychotic features
3. Current alcohol or substance use disorder, as defined by DSM
4. Acute suicidality or need for inpatient psychiatric hospitalization
5. Psychotic symptoms so severe as to warrant treatment with antipsychotic medications in the opinion of the patient's physician
6. Medical conditions such as current malignancy or hematological, endocrine, cardiovascular, renal, hepatic, gastrointestinal, or other non-PD neurological disease that is medically debilitating and/or CNS affecting (e.g., uncontrolled diabetes mellitus or thyroid disease). If there is a history of such disease and it has been stable for > one year, then subject may be included if investigator judges their participation as safe.
7. Patient currently treated with psychotherapy for anxiety/depression
8. Current treatment with another dopamine agonist

## 6. Drugs/ Substances/ Devices

- a. The rationale for choosing the drug and dose or for choosing the device to be used.

Rotigotine is an evidence-based treatment for motor symptoms and motor complications of treatment in PD and deemed to be of "acceptable risk without specialized monitoring". Dosing will begin at baseline on day zero with either 1) placebo or 2) rotigotine at 2mg/24hrs and will be increased following the recommended dose escalation schedule for PD such that subjects will increase to 4mg/24hrs in week 2, and 6mg/24hrs in week 4.]\* This dose of rotigotine is within the range shown to be safe and efficacious for the treatment of motor symptoms in PD.

- b. Justification and safety information if FDA approved drugs will be administered for non-FDA approved indications or if doses or routes of administration or participant populations are changed.

N/A

- c. Justification and safety information if non-FDA approved drugs without an IND will be administered.

N/A

## 7. Study Statistics

- a. Primary outcome variable. Hamilton Anxiety Rating Scale(HAM-A)
- b. Secondary outcome variables. 17-item Hamilton Depression Rating Scale (HAM-D), 19symptom wearing-off questionnaire (WOQ-19), Schwab and England Scale (SE), MDS-UPDRS part III
- c. Statistical plan including sample size (n=200) justification and interim data analysis.  
For objective 1: We will conduct a latent profile analysis (LPA) using the following observed variables (measured in the on-state) as latent profile indicators: age of PD onset, LEDD, HAMA, HAM-D, WOQ-19, SE, UPDRS part III, and MoCA score, to model unobserved (i.e. latent) profiles. LPA is a type of latent class analysis that uses continuous indicator variables. Using LPA we will determine 1) the number of classes/profiles that best fits symptom profiles of observed values, 2) the proportion of the sample that belongs in each class/profile (e.g. class prevalences), and 3) the means of each latent profile, conditioned upon membership in each class. We will then test whether specific subject characteristics (age, gender, variability of symptoms between on- and off-states (as change scores), and motor fluctuations), from the battery above predict differential membership in the identified latent profiles via latent profile regression. With latent profile regression, predictors of latent profile membership are modeled via multinomial logistic regression. Statistical power for latent profile regression was determined via monte carlo simulation,(42) assuming 3 classes/profiles with prevalences of 30%, 10%, and 60%. We would have 80% or greater power to detect a log odds ratio for an association between a standardized predictor and latent profile membership of 1.17 for profile 1 (prevalence of 30%) and 1.71 for profile 2 (prevalence of 10%), with profile 3 as the reference class. Antidepressant, anti-anxiety, and other psychiatric medication use will be controlled for in the analysis.

For objective 2: The primary outcome variable is the HAM-A. Power was calculated based on an enrollment of 60 subjects total, equally distributed between treatment and control groups, with a 10% dropout by the final time-point, and a standard deviation of 8.55 (which is a pooled estimate calculated from different anxiety subtypes in PD patients assessed using the HAMA).(43) The within subject/between time-point correlation was assumed to be 0.5 with a compound symmetric correlation structure, and the alpha level was set at .05. Power calculations were based on the formula of Jung and Ahn,(44) which calculates power for the difference in slope (i.e. the difference in response trajectory) between treatment and control groups for a longitudinal clinical intervention. Based on the assumptions specified, we would be able to detect an effect size of .69 from baseline to 8 weeks for the two groups with 80% power. This proposal is for a proof of concept study that will provide important initial estimates which may be used to 1) assess the potential efficacy of this novel anxiety intervention and thus provide necessary data for a "go-no-go" decision for a more definitive hypothesis-testing trial, and 2) provide estimates of effect size and variance needed to properly design such a trial.

Screening for objective 1: Screen failures are expected to be rare for objective 1 as there are only 3 criteria for exclusion: 1) UK Brain Bank criteria for PD, 2) English speaking, and 3) nondemented. In our longitudinal study of Parkinson's disease, which has autopsy confirmation at study end, the rate of accurate clinical diagnosis of PD is approximately 90%. The presence of dementia has a similar accuracy and will be further screened using the MoCA with a cut off of <23. The drop-out rate is also expected to be low as objective 1 takes place in one 3-hour visit. Screening for objective 2: Objective 2 will require 60 subjects who *can* be recruited from the n=200 from objective 1. Based on our preliminary data, 30% of subjects with a DSM anxiety disorder and comorbid depression and up to 53% with anxiety disorders only will not be

on any treatment for anxiety. In addition, we have included a protocol for enrolling individuals whose anxiety is not adequately controlled on their current therapy.(item 4 inclusion criteria)

Subjects for objective 2 will be preferentially recruited from objective 1 for maximum efficiency. In the unlikely event that none of the subjects for objective 2 come from objective 1 the total number of subjects needed for both is n=260. We will be conducting post consent screening and will allow for ~15% screen fail rate and estimate that the maximum number of subjects consented will not exceed 300.

d. Early stopping rules.

Participants will be removed from the study if they request removal, if the team believes it is unsafe to continue, if they experience significant distress for any reason, or if the patient becomes imminently suicidal. Subjects will be monitored closely by an experienced clinical team, available 24-hours per day.

